## Abstract

Title	A Phase 2 Study of Apalutamide Plus Cetrelimab in Patients with Treatment-Emergent Small Cell Neuroendocrine Prostate Cancer
Study Description	Phase 2 single arm, Simon two stage evaluation of the combination of apalutamide plus cetrelimab in patients with mCRPC and histologic and/or genomic evidence of treatment-emergent small cell neuroendocrine prostate cancer who have previously progressed on at least one prior androgen signaling inhibitor. The primary study endpoint is composite response rate as defined by PSA50 response and/or objective response by RECIST 1.1 criteria.
Phase of Study	Phase 2
Investigational Products	Apalutamide, Cetrelimab
Study population	Male, adult (18 years of age and older) patients with metastatic castration resistant prostate cancer (mCRPC) with disease progression (PD) on at least one second generation androgen signaling inhibitor, including abiraterone acetate, apalutamide, darolutamide, and/or enzalutamide and evidence of treatment-emergent small cell neuroendocrine cancer (t-SCNC). All races/ethnicity are included.
Primary Objective	To determine the composite response rate as defined by achieving one or more of the following at any time point during study treatment: 
 
• PSA50, decline from baseline in serum PSA of <math>\geq 50\%</math>, confirmed by repeat measurement <math>\geq 4</math> weeks later
 
• Objective response by RECIST 1.1 criteria
 

Secondary Objectives	
 
1. To determine safety of the combination as determined by CTCAE version 5.0
 
2. To determine the median radiographic progression-free survival by PCWG3 criteria
 
3. To determine the PSA50 and PSA90 response proportion achieved
 
4. To determine the median PSA progression-free survival
 
5. To determine the median overall survival
 
6. To determine the objective response rate and median duration of response by RECIST 1.1 criteria
 

Sample Size	N = 24 patients.

Duration of Study Treatment	Participants may continue study treatment from the time of treatment initiation until confirmed radiographic PD per PCWG3/RECIST 1.1 criteria, unequivocal clinical progression, unacceptable toxicity, or patient withdrawal, whichever occurs first – for a maximum of 24 months.
Duration of Follow Up	Safety Follow up: 30 days Safety Follow-up: 100 days  Long Term / Survival Follow up: Patients will be followed for overall survival every 90 days (+/- 30 days) from last dose of study treatment, until death, withdrawal of consent, or the end of the study, whichever occurs first.

## List of Abbreviations

ADT	androgen deprivation therapy
AE	adverse event
ALP	alkaline phosphatase
ALT	alanine aminotransferase
AR	androgen receptor
ARPI	androgen receptor pathway inhibitors
AST	aspartate aminotransferase
BET	Bromodomain extraterminal protein
BUN	blood urea nitrogen
CBC	complete blood cell (count)
CNS	central nervous system
CR	complete response
CRF	case report form
CT	computerized tomography
CTCAE	Common Terminology Criteria for Adverse Events
CTMS	Clinical Trial Management System
DSMC	Data and Safety Monitoring Committee
DSMP	Data and Safety Monitoring Plan
ECG/EKG	Electrocardiogram
ECOG	Eastern Cooperative Oncology Group
FDA	Food and Drug Administration
GCP	Good Clinical Practice
GFR	glomerular filtration rate
HBV	hepatitis B virus
HCV	hepatitis C virus
HDFCCC	Helen Diller Family Comprehensive Cancer Center
HIPAA	Health Insurance Portability and Accountability Act
HIV	human immunodeficiency virus
IAC	intermediate atypical carcinoma
ICF	informed consent form
ICH	International Conference on Harmonization
IDS	Investigational Drug Services (UCSF)
IND	investigational new drug application
IP	investigational product
IRB	Institutional Review Board
IV	Intravenous

## List of Abbreviations

mCPRC	metastatic castration resistant prostate cancer
MRI	magnetic resonance imaging
NCI	National Cancer Institute
PD	disease progression
PD-1	programmed cell death 1
PO	Per os (by mouth, orally)
PR	partial response
PRC	Protocol Review Committee (UCSF)
PSA	Prostate Serum Antigen
rPD	Radiographic progressive disease
SD	stable disease
SGOT	serum glutamic oxaloacetic transaminase
SGPT	serum glutamic pyruvic transaminase
SLD	Sum of longest diameters
t-SCNC	treatment-emergent small cell neuroendocrine carcinoma

## 1 Introduction

### 1.1 Background

Prostate cancer is the second leading cause of cancer death in men in the Western World, largely driven by patients harboring recurrent or newly diagnosed metastatic disease. These patients have a rapid and favorable response to androgen deprivation therapy (ADT). However, most patients inevitably develop hormone refractory disease, termed metastatic castration resistant prostate cancer (mCRPC). Over the last decade, there has been an expansion of therapies for patients with mCRPC beyond traditional cytotoxic chemotherapies, including novel androgen receptor (AR) pathway inhibitors (ARPI) that more completely ablate androgen signaling such as abiraterone acetate, enzalutamide, and apalutamide (Beer et al., 2014; de Bono et al., 2011; Fizazi et al., 2012; Ryan et al., 2015, 2013; Scher et al., 2012; Smith et al., 2018), sipuleucel-T, an autologous cellular immunotherapy targeting prostatic acid phosphatase (PAP) (Kantoff et al., 2010), and radium-223, a bone-targeting alpha emitter (Parker et al., 2013). Despite these therapeutic advances, many patients on mCRPC eventually succumb to their disease, often due to acquired tumor resistance to these novel agents. In particular, there remain few treatment options for men with mCRPC refractory to the ARPI. Therefore, there is a great need to develop clinically efficacious, well-tolerated, novel therapies for this patient population.

### 1.2 Transdifferentiation is an Adaptive Response to Long-term ADT

There is marked heterogeneity across mCRPC patients with widely varying clinical outcomes and therapeutic responses driven largely from diverse mechanisms of resistance to overcome androgen-signaling inhibition. Transdifferentiation to a neuroendocrine phenotype, termed treatment-emergent small cell neuroendocrine prostate cancer (t-SCNC), represents a highly aggressive and lethal subset of prostate cancer that is becoming increasingly common in previously treated mCRPC. While *de novo* SCNC represent 1-2% of new cases, in our prospective, multi-institutional study of over 200 unselected mCRPC patients previously treated with ARPI, treatment-emergent SCNC (t-SCNC) was identified in 17% of mCRPC biopsies (Aggarwal et al., 2018). Compared to mCRPC with adenocarcinoma features, t-SCNC is characterized by decreased AR signaling, enrichment for loss of *RB1* and *TP53*, and enrichment of activation of transcriptional factors including *EZH2*, *POU3F2*, *ASCL1*, among others.

It is hypothesized that t-SCNC arise clonally from adenocarcinoma, though through which molecular mechanisms, i.e. de-differentiation to a primitive progenitor or transdifferentiation from epithelial to neuronal phenotypes, remains under active investigation (Aggarwal et al., 2019; Beltran et al., 2016; Guo et al., 2011; Zou et al., 2017). Importantly, patients with t-SCNC exhibit poor prognoses compared to mCRPC with adenocarcinoma (Aggarwal et al., 2018; Small et al., 2016). Furthermore, patients with t-SCNC have limited effective treatment options outside of traditional platinum-based chemotherapies, which itself have limited durability of response and carry significant risk of undesired side effects (Aparicio et al., 2013). In the Aparicio et al. study, 97% of patients treated with platinum therapy experienced progression of disease with a median time of 3.0 months. Therefore, there is an unmet clinical need to develop new, durable therapies for these two high-risk mCRPC subtypes.

Identification of t-SCNC currently relies on histologic evaluation of a metastatic tumor biopsy, which can be difficult to obtain in patients owing to the sclerotic nature of this bone-tropic disease entity. Contrary to the classic clinical characteristics of *de novo* t-SCNC, the presence of visceral metastases or elevation of serum neuroendocrine markers does not reliably identify t-SCNC on paired tumor biopsies. Several clinical and/or genomic hallmarks enrich for the identification of t-SCNC, including the presence of *RB1* genomic loss on somatic tumor profiling, as well as the presence of low PSA secretion in relation to metastatic disease burden.

Among 183 evaluable patients, low PSA secretion (PSA < 5 ng/mL) with concomitant high metastatic disease burden (> 5 metastases on conventional imaging) was found in 15 patients (8%) and was associated with enrichment for t-SCNC transcriptional signature, low AR transcriptional activity. *RB1* genomic loss is enriched in t-SCNC vs. adenocarcinoma biopsies (Aggarwal et al. JCO 2018) and is likewise associated with significant shortened survival (Chen et al. Eur Urol 2019).

[figure not shown]

Figure 1.2 AR Transcriptional Signature Score and T-SCNC Signature Score

### 1.3 Activity of Immune Checkpoint Inhibition in Unselected mCRPC Alone and in Combination with AR Pathway Inhibition

In patients with unselected mCRPC, pembrolizumab has modest anti-tumor activity, but durable responses can be achieved in a minority of patients. In the recently reported updated analysis of the KEYNOTE-199 study of mCRPC patients who had previously received docetaxel, the objective response rate in patients with measurable disease was 5% and 3% in those with PD-L1 positive and negative tumors, respectively (Antonarakis et al. 2019). Duration of responses lasting  $\geq$  12 months was 71% and 50%, respectively, in the two cohorts. The PSA50 response rate was 11% overall, and there did not appear to be an enrichment of response in PD-L1 positive vs. negative tumors.

[figure not shown]

Figure 1.3 Change from Baseline in PSA, Cohorts 1+2+3

Pembrolizumab combined with AR targeted therapy may lead to increased response rate however this has not been definitively demonstrated in a randomized trial setting. In a single arm study (KEYNOTE-365, Cohort C) of pembrolizumab plus enzalutamide in abiraterone

acetate-resistant, chemotherapy-naïve mCRPC, the PSA50 response rate was 27% (18/67 patients), and the objective response rate was 20% (5/25 patients with measurable disease) ([name] P, et al. 2019).

#### **1.4 Immunogenicity of t-SCNC compared to adenocarcinoma without neuroendocrine features and clinical activity of immune checkpoint blockade in high grade neuroendocrine cancers**

The immunogenicity of mCRPC tumors, including the mutation burden, tumor infiltrating lymphocytes, and expression of T-cell regulatory checkpoint molecules like PD-1 and PD-L1 are low in an unselected population of prostate tumors compared to other tumor types that show a higher response rate to checkpoint blockade, like melanoma (Haffner et al., 2018). PD-L1 expression strongly correlates with objective response to anti-PD-1 therapy (Taube et al., 2014). However, only 14% of mCRPC patients in the KEYNOTE-028 study examining pembrolizumab in this patient population screened positive for PD-L1 expression. Recent work has demonstrated that PD-L1 expression was higher in patients with t-SCNC compared to mCRPC without evidence of neuroendocrine features (Ferguson et al., 2019; Nappi et al., 2019). This suggests that de-differentiated t-SCNC have increased immunogenicity and may have a better response rate to anti-PD-1 therapy compared to mCRPC cases without neuroendocrine features.

The efficacy of immune checkpoint inhibition in high grade neuroendocrine cancers is supported by recent clinical efficacy and accelerated FDA approval for nivolumab in small cell lung cancer (Antonia et al. Lancet Oncology 2016). An objective response was achieved in ten (10%) of 98 patients receiving nivolumab 3 mg/kg, one (33%) of three patients receiving nivolumab 1 mg/kg plus ipilimumab 1 mg/kg, 14 (23%) of 61 receiving nivolumab 1 mg/kg plus ipilimumab 3 mg/kg, and ten (19%) of 54 receiving nivolumab 3 mg/kg plus ipilimumab 1 mg/kg.

In extrapulmonary high grade neuroendocrine cancers, immune checkpoint inhibition has shown preliminary evidence of activity. In the neuroendocrine tumor cohort of the basket DART study, the objective response rate with combination of ipilimumab + nivolumab was 44% in the subset of patients with high-grade disease.

#### **1.5 Cetrelimab in Prostate and Other Solid Tumor Malignancies**

Cetrelimab (JNJ-63723283) is a fully human immunoglobulin G4 (IgG4) kappa mAb containing the hinge-stabilizing S228P mutation. This mutation prevents the fragment antigen binding (Fab) arm exchange that normally occurs with IgG4 antibodies. Cetrelimab binds to PD-1 with high affinity and specificity, blocks binding to both PD-L1 and PD-L2 ligands, enhances pro-inflammatory cytokine production from ex vivo stimulated T cells, and reduces tumor volume in a number of preclinical models in vivo.

Study 63723283LUC1001 is an ongoing, multicenter, Phase 1/2 FIH study of cetrelimab in subjects with advanced solid tumor malignancies. Part 1 of the study, initiated on 21 November 2016 (date of consent of the first eligible subject), consists of dose escalation cohorts and PK/PD cohorts. Part 1 established the recommended Phase 2 dose (RP2D), which may be administered at either 240 mg once every 2 weeks (q2w) or 480 mg once every 4 weeks (q4w). In Part 2, initiated on 03 May 2017 (date of consent of the first eligible subject), this RP2D is being evaluated in selected solid tumor types, including non-small cell lung cancer (NSCLC), melanoma and high-level microsatellite instability (MSI-H) or mismatch-repair deficiency (dMMR) colorectal cancer (CRC). The purposes of dose expansion in Part 2 are to further characterize the safety and to assess the antitumor activity of the RP2D.

As of the clinical safety and efficacy data cutoff date of 02 September 2019, a total of 204 subjects have received at least 1 dose of cetrelimab. The age of enrolled subjects ranged from

23 to 86 years. The majority of subjects treated with cetrelimab had Stage III or IV malignancy at the time of initial diagnosis and metastatic disease at study entry, consistent with the protocol-specified requirements of metastatic or unresectable advanced cancers. The number of prior regimens of anticancer therapy ranged from 1 to 12, with a median number of 2 prior therapies. As of the clinical safety data cutoff date, the duration of cetrelimab treatment ranged from 1 to 28.5 months, with a median treatment duration of 3.25 months. The number of doses administered ranged from 1 to 63.

The RP2D of 240 mg q2w was determined based on interim safety, PK, and PD data as of 27 April 2017. The additional interim safety, PK and PD data as of September 2017 support an alternate regimen, namely 480 mg q4w, with the same total dose as RP2D of 240 mg q2w but given with a longer dosing interval which enables flexibility of drug administration in various clinical settings. Selection of the RP2D of 240 mg q2w and 480 mg q4w was based on the following:

- No maximum tolerated dose has been identified with administration of doses up to 460 mg q2w and 480 mg q4w and doses were well tolerated (Section 4.4).
- Cetrelimab demonstrated comparable preclinical in vivo TGI and comparable in vitro activity across various assays as the approved PD-1 inhibitors nivolumab and pembrolizumab (Section 3.1.1). Therefore, similar clinical efficacious target concentrations would be expected for cetrelimab.
- Based on preliminary PK data, the median observed near-steady state Cmin for cetrelimab at 240 mg q2w is 44.8 µg/mL (N=5, trough concentration before the fifth dose). This is comparable to the Cmin,ss reported for nivolumab (57 µg/mL) and pembrolizumab (23 µg/mL) at their approved doses (240 mg q2w for nivolumab and 2 mg/kg or 200 mg q3w for pembrolizumab).
- The median steady state Cmin,ss for cetrelimab at 480 mg q4w is expected to be approximately 42 µg/mL, based on an observed median Cmin after first dose at 30 µg/mL and predicted accumulation ratio of ~1.4 based on preliminary PK modeling. The Cmin,ss from 240 mg q2w and 480 q2w is therefore expected to be comparable, and in range with other anti-PD-1 agents nivolumab and pembrolizumab at their approved clinical dose.
- Administration of cetrelimab resulted in saturation of PD-1 RO on circulating CD3+ T cells at all administered doses (80 to 480 mg) and dosing frequencies (q2w and q4w).

In subjects receiving the RP2D of 240 mg IV every 2 weeks in the cetrelimab monotherapy study (Study 63723283LUC1001; NCT02908906), the observed ORR (CR+PR) was 21.9% (32/146) in all subjects evaluable for response. Five of the 146 (3.4%) subjects (all with melanoma) demonstrated a complete response (CR) and 27 (18.5%) had a partial response (PR) as assessed by the investigator. Overall, 29 (19.9%) subjects receiving cetrelimab had stable disease (SD).

Overall, 207 (97.2%) of the 213 subjects who received treatment experienced at least 1 TEAE. One hundred forty-two (142, 66.7%) subjects experienced TEAEs considered to be possibly, probably, or very likely related to cetrelimab administration by the investigator. Across all dose cohorts, the most frequently reported TEAEs (≥10% of subjects) were as follows: asthenia (24.4%), fatigue (20.7%), dyspnea (20.2%), pyrexia (19.7%), diarrhea (18.8%), anemia, decreased appetite, and nausea (17.8% each), cough (17.4%), back pain (15.5%), aspartate aminotransferase (AST) increased and vomiting (13.1% each), alanine aminotransferase (ALT) increased (12.7%), abdominal pain (11.7%), constipation (11.3%), and arthralgia and rash

(10.3% each). In the 161 subjects receiving 240 mg q2w, the most frequent TEAEs ( $\geq 10\%$  of subjects) were as follows: asthenia (27.9%), dyspnea, diarrhea, and pyrexia (21.8% each), cough (20.0%), fatigue and decreased appetite (18.2% each), anemia (17.6%), nausea (17.0%), ALT increased (15.2%), AST increased (14.5%), and back pain (15.8%).

Overall, Grade 3 or higher TEAEs were experienced by 113 (53.1%) of the 213 subjects in the monotherapy studies (Table 26). The most frequently reported Grade 3 or higher TEAEs ( $\geq 2\%$  of subjects) were as follows: anemia (7.0%), dyspnea (5.6%), GGT increased (4.7%), hyponatremia (4.2%), AST increased and hyperamylasemia (3.3% each), ALT increased, hypertension, fatigue and lipase increased (2.8% each), pleural effusion, abdominal pain and general physical health deterioration (2.3% each), and urinary tract infection, neutropenia, blood alkaline phosphatase (ALP) increased, asthenia, and hyperbilirubineamia (1.9%).

Overall, 71 (33.3%) of the 213 subjects treated in the monotherapy studies experienced treatment-emergent irAEs as assessed by the investigator. The most commonly reported irAEs ( $> 2\%$  of subjects) included hypothyroidism (6.1%), rash (4.7%), asthenia (4.2%), hyperthyroidism and dyspnea (3.3% each), pruritus and diarrhea (2.8% each), and pneumonitis (2.3%). Nine (9, 4.2%) subjects experienced irAEs that led to treatment discontinuation: pneumonitis in 3 subjects, and myocarditis, hyperthyroidism, autoimmune colitis, hepatotoxicity, ALT increased, GGT increased, myopathy, and myasthenia gravis in 1 subject each.

PK/PD and immunogenicity data are presented in the Investigational Brochure.

## 1.6 Combination of Apalutamide Plus Cetrelimab

Study 56021927PCR2032 (NCT03551782) is an ongoing, multicenter, apalutamide Phase 1b study of subjects who currently have mCRPC and who have progressed on therapy with abiraterone acetate plus prednisone/prednisolone (AA-P), apalutamide, or enzalutamide. The study was initiated on 2 July 2018 (date of first subject consent). As of the clinical data cutoff date of 02 September 2019, a total of 27 subjects have received at least 1 dose of apalutamide in combination with cetrelimab. The combination was overall deemed tolerable with no dose-limiting toxicities noted. Grade 3 or higher treatment-emergent adverse events (AEs) included: rash (37.0%), and fatigue/asthenia (14.8%). Overall, AEs leading to treatment discontinuation occurred in 6/27 patients (22.2%), including three patients with rash, one patient with hypersensitivity reaction, one patient with serum sickness, and one patient with asthenia.

## 1.7 Rationale for the Continuation of Androgen Receptor Blockade in Transdifferentiated Prostate Cancer

Despite the low AR transcriptional activity of treatment-emergent small cell neuroendocrine prostate cancer, there is persistent AR expression observed in the majority of t-SCNC biopsies (Aggarwal et al. JCO 2018). This indicates that epigenetic dysregulation leads to reprogramming away from an AR-driven transcriptional program. Therefore, continuation of AR blockade in the form of apalutamide may provide additive benefit compared to immune checkpoint blockade alone.

## 2 Study Objectives

### 2.1 Hypothesis

We hypothesize that the combination of apalutamide plus cetrelimab will achieve a clinically significant composite response rate with sufficient durability of response in mCRPC patients with evidence of treatment-emergent small cell neuroendocrine prostate cancer.

## 2.2 Primary Objective and Endpoints

Primary Objective	Endpoints	Time Frame
To determine the composite response rate (achieving one or more of the endpoints) of apalutamide plus cetrelimab.	

PSA50 (decline from baseline in serum PSA of <math>\geq 50\%</math>, confirmed by repeat measurement <math>\geq 4</math> weeks later)* AND/OR

Objective response by RECIST 1.1 criteria**

	From initiation of study treatment until discontinuation of treatment (maximum of 2 years).

\* to be considered evaluable for PSA50 response, patients must have baseline PSA level  $> 2$  ng/mL

\*\* to be considered evaluable for objective response, patients must have measurable soft tissue disease by RECIST 1.1 criteria on baseline scan assessment

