#### **6.3.4 30-day Safety Follow Up (+/- 7 days)**

- Clinical Assessments
  - AE assessment (may be performed via telephone)
- Laboratory Assessments
  - Hematology labs - CBC with differential and platelet count
  - Blood chemistry assessment, including: ALP, ALT/AST, total bilirubin, calcium, BUN, creatinine, potassium, sodium, chloride, bicarbonate

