#### Evaluation of Post-treatment PSA changes

All patients will be evaluated for PSA decline. Patients with disease that is not measurable will be eligible for this study and will be assessed for response based on changes in PSA and serial bone scans (if appropriate). The baseline serum PSA must be at least 2 ng/mL to be evaluable for PSA response.

- 50% and 90% PSA Decline: PSA decline of at least 50% and 90%, respectively, from baseline confirmed by a second measurement at least 3 weeks later. The reference for these declines should be a PSA measured within 2 weeks prior to starting therapy.
- PSA Progression: Prostate Cancer Working Group 3 (PCWG3) Criteria will be reported. PSA progression occurs when the PSA has increased 25% or greater above nadir and an absolute increase of 2 ng/mL or more from the nadir is documented. Where no decline is observed, PSA progression similarly occurs when a 25% increase from baseline value along with an increase in absolute value of 2 ng/mL or more. PSA progression (without evidence of progression on scans) will not be criteria for discontinuation of study therapy.
- PSA Response Duration: The PSA response duration commences on the date of the first 50% decline in PSA. The response duration ends when the PSA value increases by 25% above the nadir, provided that the increase in the absolute-value PSA level is at least 5 ng/mL or back to baseline, whichever is lower
- Progressive disease by PSA is defined by PSA progression, noted above.

- Time to PSA Progression: The start of the time to PSA progression is the day treatment is initiated. The end date is the date of the first PSA rise over the determined PSA PD value.

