#### 8.3.2 Primary Analysis (or Analysis of Primary Endpoints)

The composite response rate is the primary endpoint of the study, defined as:

- $\geq 50\%$  decline from baseline PSA (defined by C1D1 value), confirmed by repeat measurement  $\geq 3$  weeks later AND/OR
- Objective tumor response by RECIST 1.1 criteria AND/OR

The composite response rate along with 95% confidence interval will be reported.

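### A PSA50 first seen at, or shortly before, End of Treatment has no assured confirming sample, because the primary response window closes at discontinuation and no later PSA is scheduled

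*Combined protocol and SAP*

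**What the plan says.** **Window.** Section 2.2 sets the time frame of the composite response as "From initiation of study treatment until discontinuation of treatment (maximum of 2 years". The Abstract defines it as "achieving one or more of the following at any time point during study treatment".

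**Confirmation.** The Abstract, 2.2, 2.3 and the Secondary Objective 3 text in 8.3.3 require a repeat PSA at least 4 weeks later. The PSA subsection of 7.1.4 has the decline "confirmed by a second measurement at least 3 weeks later", and 8.3.2, which governs the primary analysis, also uses 3 weeks.

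**PSA schedule.** Sections 6.1 and 6.3 list serum PSA at Screening, Day 1 of every cycle and End of Treatment. No day or window is given for the End of Treatment visit. The 30-day visit (6.3.4) lists "Hematology labs - CBC with differential and platelet count" and chemistry, but no PSA. The 100-day visit and survival follow-up (6.3.5, 6.3.6) have none either.

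**Denominator.** Section 8.3.1 includes every patient with a Screening PSA above 2 ng/mL and/or measurable disease. No text says how an unconfirmed PSA50 is scored, or whether a PSA taken at or after discontinuation may confirm one.

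**The concern.** The definition needs two PSA values several weeks apart, while the window and the schedule both end when treatment does. A decline that first appears near the end of treatment may therefore have no second scheduled value. The patient is not removed from the analysis, so the missing sample turns into a non-response.

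Early stops are foreseeable. Section 1.6 reports that 6 of 27 patients (22.2%) in the phase 1b study of this combination discontinued because of adverse events, three of them for rash. The RECIST route offers little help to a patient who stops very early. The first scheduled scan is at C4D1 with a 14-day lead, End of Treatment lists no imaging, and a patient without measurable disease can respond only by PSA.

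The decision rule has little slack: the trial stops at 2 or fewer responses in 14 and rejects the null at 8 or more in 24.

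**Working it through.** **1. Timing on the protocol's own calendar**

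- Day 1 PSAs are nominally 28 days apart. With a ±3-day window on each visit, the gap is 22 to 34 days.
- A PSA50 first seen at the last Day 1 visit is confirmable only if the End of Treatment PSA falls at least 28 days later (2.2) or at least 21 days later (7.1.4, 8.3.2). It must also be accepted that this value may count.
- A PSA50 first seen at End of Treatment has no later scheduled PSA.

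Example: PSA halves at C2D1 (day 29), and both drugs are permanently stopped on day 35, with End of Treatment that day. The gap is 35 − 29 = 6 days, so there is no confirmation. The 30-day visit falls 23 to 37 days after the last dose, on days 58 to 72. That is 29 to 43 days after the first value and satisfies both the 3-week and the 4-week rule.

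Counter-example: the same patient is put on hold on day 35 instead. A 28-day hold ends on day 63. C3D1 is day 57, which is 57 − 29 = 28 days after C2D1. If the visit calendar is kept during the hold, the confirming PSA is taken.

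**2. The plan's own design figure (8.1.1)**

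Inputs: n1 = 14, stop if 2 or fewer responses; n = 24, reject if 8 or more; p0 = 0.15; p1 = 0.40.

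P(reject | p) = Σ over x = 3 to 14 of P(X1 = x) × P(X2 ≥ 8 − x), with X1 ~ Bin(14, p) and X2 ~ Bin(10, p).

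- At p = 0.40 this gives 0.8024, which reproduces the stated 80.2%.
- At p = 0.15 it gives 0.0194. The stated 0.025 fits as the design's ceiling, not the attained value: a search with alpha at most 0.025 and power at least 0.80 returns this same minimax design.

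**3. Illustration of lost confirmations**

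Let f be the share of composite responders who would have been confirmed had a sample been taken, were not, and have no RECIST response. The documents give no value for f, so those below are assumptions. The scorable rate is 0.40 × (1 − f). The last column applies the same loss to the null rate, 0.15 × (1 − f).

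| f (assumed) | Scorable rate | Power | Stage 1 stop at true 40% | Type I error, null diluted alike |
|---|---|---|---|---|
| 0 | 0.400 | 80.2% | 4.0% | 0.0194 |
| 2.5% | 0.390 | 77.4% | 4.7% | 0.0168 |
| 5% | 0.380 | 74.3% | 5.4% | 0.0145 |
| 10% | 0.360 | 67.4% | 7.3% | 0.0106 |

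If the null rate is not diluted, type I error stays at 0.0194. It does not rise in either case.

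**The case against.** A reader might infer that any PSA50 followed by a toxicity stop cannot be confirmed, so that a true responder is counted as a failure. The documents do not support that, for four reasons.

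- **Most rash is handled by a hold.** Section 5.4 provides holds of up to 28 days for Grade 2 rash (at investigator discretion) and Grade 3 or higher. As shown above, such a hold can reach the next Day 1 PSA. Section 5.2 also lets one drug continue when the other is stopped. The exposed cases are chiefly immediate stops of both drugs, such as the desquamation, blistering or mucosal cases in 5.4, and withdrawals.
- **The End of Treatment PSA may itself confirm.** Its day is not fixed, 8.3.2 needs only 3 weeks, and 8.3.2 sets no limit on when the confirming value is taken. That the 2.2 time frame excludes a later confirming value is one reading, not stated text.
- **An unconfirmed decline is not a proven response.** Confirmation exists to exclude transient falls, and requiring it on treatment is a defensible conservative choice.
- **The 40% alternative can be read as already a confirmed rate.** Section 8.1.1 points to the 8.3.2 definition. On that reading the power is 80.2% as stated, and the table describes a loss only relative to a 40% rate that full sampling would have confirmed.

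A reader might also apply the 22.2% discontinuation rate as the loss. That gives 0.40 × (1 − 6/27) = 0.311 and power of 47.7%. This is an extreme bound, not an estimate. It would need every adverse-event stop to fall between first decline and confirmation, with no RECIST response in any of those patients. Section 1.6 gives neither the timing of the stops nor whether one or both drugs were stopped.

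All of this narrows the affected group. It does not supply the missing sample for those who remain in it.

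**Conclusion.** The gap is real but limited. A PSA50 first seen at End of Treatment, or less than the confirmation interval before it, has no assured scheduled confirmation. Scoring such a patient as a non-responder, absent a RECIST response, follows from the definition in 8.3.2 and the denominator in 8.3.1; no explicit rule says so.

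The effect is conservative: possible loss of power and a slightly higher chance of stopping at stage 1, with no inflation of type I error. The size is unknown. The falls to 74.3% and 67.4% rest wholly on assumed losses of 5% and 10%, and on treating 40% as the rate that complete sampling would confirm. The conflict between the 3-week and 4-week intervals needs no such assumption and should be resolved in any case. The point merits a change because the remedy costs almost nothing, not because a large loss has been shown.

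**What to change.** 1. Add serum PSA to the 30-day safety follow-up laboratory tests in 6.1 and 6.3.4.
2. State in 2.2 and 8.3.2: *A PSA50 first reached on treatment may be confirmed by a PSA at End of Treatment or up to the 30-day safety visit, provided that the confirmation interval is met and no new anticancer therapy has started. A PSA50 not so confirmed is scored as no PSA response.*
3. Use one confirmation interval in the Abstract, 2.2, 2.3, 7.1.4, 8.3.2 and 8.3.3.
4. Give the End of Treatment visit a window, and state one starting point for the 30-day visit: 3.6 counts from End of Treatment, 6.1 from the last dose.

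**Cost.** One assay in at most 24 patients, on blood already drawn, plus a few sentences. The adverse event review at that visit may be done by telephone, but the blood tests are scheduled regardless.

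**Limits.** Some confirming values will be taken off drug. Coverage is also incomplete for a decline first seen at End of Treatment. Counted from that visit, the 30-day visit falls on days 23 to 37, which always meets 21 days but meets 28 days only from day 28 on. Counted from an earlier last dose, neither interval is assured.
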